3.6 Quantitative data collection

Foams register and explain changing in life style factors and work participation. The physical test may say something about the participant's physical capacity. In this study foams and a test will measure conditions that affect socio- economic, demographic and individual factors, their expectation of returning to work, the motivation for working and sick-leave, physical activity, physical and mental health, diet and nutrition, and life quality. Information about the date of the stay, diagnoses, and activity is in the journal at Muritunet.

Areas	Time of data collection	Foams
Employment data	BL	ARR foam, socio-demographic data and work status (Nasjonal kompetansestest for arbeidsretta rehabilitering)
	BL, T1 and T2	Short ARR foam
	BL	Return to work self- efficacy (RTWSE 19) [31]
Health data	BL	High, waist circumference, body fat percentage and fat-free mass kg
	BL, T1, and T2	Weight, BMI
	BL	Diagnoses
	BL	Subjective Health Complaints (SCH 25) [32].
Physical capacity	BL	Step-test with Borg scale CR 10
	BL, T1, and T2	Registration of level of physical activity(Health Directorate)
Quality of life	BL, T1, and T2	Quality of life (15D) [33].
Food habits	BL	Thoughts and feelings about food, body and eating behavior. Survey about Binge eating disorder (EDO)[34].
	BL, T1, and T2	Food behavior registration (Health Directorate)

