1.3 Background

In 2015 established HMN RHF an occupational rehabilitation program for people with BMI above 30 who might be or is on sick leave directly or indirect cause obesity. This program combines work participation and life style changes and exists only in two institutions in Norway. The goal of the program is to increase function and work ability and weight loss. The program is new, and few documents exist on the effect and the correlation between life style changes and work ability. There is also need to question whether obesity is the reason for work absence or is there other factors that affect work ability. This study wants to follow up a group of people who have been participating occupational rehabilitation at Muritunet.

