The primary goal of this trial: What correlation is there between life style changing and work participation after participating in occupational rehabilitation on Muritunet?

Aims of the trial are:

1. Will changes in physical activity, diets, and life quality correlate with work participation?
2. Will changes in physical activity, diets, and return to work self-efficacy correlate with life quality?
3. Will changes in work participation, life quality, and diets correlate with weight changes?
4. What experience the participants as important factors to achieve lifestyle changes and work participation?

Work participation defined in this study is working full time or partial with an employer, permanent or temporary or as a student. The employee has to work coherently in 28 days without to receive social benefits.

Life quality defines in either in a subjective or an objective perspective [29]. In this study, the subjective perspective emphasizes the individual's positive, negative, cognitive and emotional experience that concern life quality.

Diet in this study is the intake of food and liquid that shall ensure a satisfying amount of calories, nutrient and prevent life style diseases.

Physical activity in this study is action made by musculature in a way that it results in increased energy consumption higher than resting.

3 Implementation

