3.3 Recruiting of participants

Recruiting participants in this study are as followed:

1. Before the first stay at Muritunet. The patients will receive an envelope with written information by post a month before their stay. In the envelope, there are two letters. One with detailed information about the study and one letter with a request to consent to the research. After the participants arrive Muritunet, they will receive information about the study, attachment one, given by project secretary. Those who want to participate in the study gives written consent. The project secretary registers the written consents in SPSS at Muritunet. SPSS is a comprehensive software package for statistical analysis and data management.
2. For participants who participate or are finished with the stay at Muritunet. The participants receive by post a written letter with detailed information about the study and two letters with a request to consent in the study. In addition to the letters, there is a prepaid envelope with the address to Muritunet, attachment one. If the person approves to participate in the study, he or she signs the consent and returning it to Muritunet. The project secretary registers the agreement in SPSS. This registration goes to the researcher who can call the participant regarding interview.

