3.4 The content of the occupational rehabilitation stay at Muritunet

The participants report data while they are at Muritunet. The rehabilitation stay is as followed with the moment for data collection:

1. Four weeks with an institutional stay at Muritunet (BL)
2. Follow-up:
 - a. Eight weeks, telephone contact between therapist at Muritunet and the participant.
 - b. 16 weeks, video conference on SKYPE between all the participants and a therapist. Lecture on diets.
 - c. 28 weeks, Outpatient stay at Muritunet. Central themes that day is education, conversation, physical test, and forms. (T1)
 - d. 40 weeks, telephone contact between therapist at Muritunet and the participant.
 - e. 52 weeks, Outpatient stay at Muritunet. Central themes that day is education, conversation, physical test, and forms. (T2)

The participants in the occupational rehabilitation program get both practical and theoretical intervention, in groups and individual. Four main themes; cognitive therapy, physical activity, diets and focus on work-oriented approach. The table under shows both groups based activity and personal follow-up.

Group based intervention	In stay	Time	Follow- up	Time
Cognitive approaches in groups	
 - Expectation clarification - Sleep - Cognitive methods - Values, will and choice - Goals setting - Motivation - To come home/ what next/ home - Acceptance and commitment therapy 	11t 2x 1,5 t	Exchange of experience (by 16, 28 and 52 weeks) Acceptance and commitment therapy (by 28 and 52 weeks)	2x 1,5 t 2x 1,5 t
Physical activity in groups	Education- how to exercise Physical activity in a group	1 t 23,5 t		
Diet	Education 
 - Diets - Food knowledge Making food in practice	2t 2,5 t 5 t	Diet, lecture- SKYPE (by 16 weeks)	2 t
Work-oriented approach	Education 
 - Rights and duties at work - Work and health. Individual follow-up	1 t 1,5 t >1 t		
Education, knowledge about obesity	Education 
 - Facts about obesity part one - Facts about obesity part two 	1 t 1 t		
Data-collection	Foams Weight and waist circumference Physical test Skype	1 t 2 t 2 t 1 t	Foams (by 28 and 52 week) Weight and waist circumference (by 28 and 52 weeks) Physical test (by 28 and 52 weeks)	2 t 2 t 2 t

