3.5 Data

This study will use several sources for data to measure changing among the participants. Data from baseline, T1 and T2 will be the foundation to see if there is a correlation between the different factors, as well as to substantiate or to find new findings.

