3.9 Analyse

The goal of this study is to explore the correlation between life style changing and work participation. Four secondary issues will result in using different ways of analyzing the data material. In this way, each issue can be investigated on their own, but also analyzed with each other.

The primary analyzing approach for this study is multivariate logistics regression analysis with a focus on the correlation between several independent variables (X) and dependent variables (Y). In the main issue Y= work, and X= physical activity (x1), diets (x2) and life quality (x3). Work divides into three categories; a) full time working, b) part time working, c) not working. In the secondary issue, is Y= life quality and X= physical activity (x1), diets (x2), and the belief in managing (x3).

In the quality research, thematic methods will be used to analyze the interviews. This method can catch the significant complexity in the text and is the most usual way to analyze a text in qualitative research. This way of analyzing consist of six steps. 1. Transcribing data, 2. Reading and re-reading the data, 3. Coding, 4. Search after subjects, 5. Define and give a name to the subjects, and 6. Choose to illustrate examples of different issues.

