3.10 Calculation of sample size

The calculation of the sample size on a group basing on previously participated in a similar occupational rehabilitation intervention for people with a BMI above 30 at Muritunet. The research question is leading for the sample size. The calculation is based on the time for data collection baseline and at the end of the intervention at Muritunet T3. The calculation is basing on apriority effect size, p value =0,05 and 80 percent statistical strength.

Goal of changing

1. Work; With a statistical power of 80,4 percent to achieve a clinical and a statistically significant change in 25 percent increasing work participation this study has to have 51 participants with two end point. The calculation is made out of 95 percent confidence interval (95% CL=18,05-31,95).
2. Weight reduction; With a statistical power of 80,2 percent to achieve a clinical and a statistically significant change in 11 kg weight reduction this study has to have 59 participants with two end point. The calculation is made out of 95 percent confidence interval (95% CL=6,82-15,18).
3. Quality of life; With a statistical power of 80,7 percent to achieve a clinical and a statistically significant change on 0,02 this study has to have 55 participants with two end point. The calculation is made out of 95 percent confidence interval (95% CL=0,025- 0,045). In the foam Quality of Life 15D, the SMR is the smallest clinical relevant change 0,015.

This calculation is done with the use of SPSS Sample Power program.

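### Aim 2 asks about change in return-to-work self-efficacy, but the schedule in section 3.6 measures it only at baseline

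*Protocol*

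**What the plan says.** Aim 2, in section 2 of the protocol, reads "Will changes in physical activity, diets, and return to work self-efficacy correlate with life quality". Section 3.9 turns this into a model: "In the secondary issue, is Y= life quality and X= physical activity (x1), diets (x2), and the belief in managing (x3"). It does not say whether x3 is a level or a change.

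Section 3.5 sets the measurement basis for the correlations: "Data from baseline, T1 and T2 will be the foundation to see if there is a correlation between the different factors".

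The table in section 3.6 then assigns time points. Three of the four aim 2 measures (the physical activity registration, the food behaviour registration and the 15D) are at BL, T1 and T2. The fourth, "Return to work self- efficacy (RTWSE 19"), is at BL only.

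Section 3.4 plans form-filling at both outpatient visits, "Foams (by 28 and 52 week"), without naming the forms. The T1 and T2 data packages in section 3.1 mention neither self-efficacy nor RTWSE-19.

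**The concern.** A within-person change needs at least two measurements, and the table gives one. If staff work from the table, x3 can only be the baseline level. The model could still be fitted, but it would ask whether people who start with more confidence have better quality of life. Aim 2 asks whether gaining confidence goes with quality of life. A result for the first question could easily be reported as an answer to the second.

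The omission cannot be repaired afterwards, because a questionnaire not given at T2 cannot be recovered. Time may already have run out for some participants. According to section 1.3, "In 2015 established HMN RHF an occupational rehabilitation program for people with BMI above 30", and section 3.3 has a recruitment route "For participants who participate or are finished with the stay at Muritunet".

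**Working it through.** **1. Aim 2 variables against the section 3.6 table**

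| Aim 2 variable | Instrument in 3.6 | Time points | Changes from baseline available |
|---|---|---|---|
| Physical activity | Activity registration | BL, T1, T2 | 2 |
| Diet | Food behaviour registration | BL, T1, T2 | 2 |
| Quality of life | 15D | BL, T1, T2 | 2 |
| Return-to-work self-efficacy | RTWSE-19 | BL | 0 |

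**2. Search for a later measurement elsewhere.** Section 3.1 lists work motivation at T1 and T2 but ties it to no instrument. Section 3.4 has unspecified forms. The short ARR form is repeated, but RTWSE-19 has its own row in the same employment block, and nothing says the ARR form contains it. The register data (3.7) and the focus groups (3.8) yield no self-efficacy score.

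**3. How well baseline could stand in for change.** Let B be the baseline score, C the change to T2, and rho the BL-to-T2 correlation, with the same SD s at both times. Then:

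- cov(B, C) = -(1 - rho)s²
- var(C) = 2(1 - rho)s²
- corr(B, C) = -sqrt((1 - rho)/2)

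The protocol gives no rho, so a range is assumed:

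| rho | corr(B, C) | Share of variance in change explained |
|---|---|---|
| 0.5 | -0.50 | 25% |
| 0.6 | -0.45 | 20% |
| 0.7 | -0.39 | 15% |
| 0.8 | -0.32 | 10% |

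Baseline and change therefore run in opposite directions, and most of the variation in change is not captured by baseline.

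**4. Who can still give a change score.** The protocol version is dated 24.7.2017, and section 3.4 puts T1 at 28 weeks and T2 at 52 weeks. Counting from admission:

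- 24.7.2017 minus 52 weeks is 25.7.2016. Anyone admitted before then is past T2.
- 24.7.2017 minus 28 weeks is 9.1.2017. Anyone admitted between the two dates is past T1 but can still give a BL-to-T2 change.

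If the weeks run from the end of the four-week stay, the admission cut-offs move back four weeks, to 27.6.2016 and 12.12.2016.

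**5. What losing those past T2 would cost.** Section 3.10 plans for the 15D that "this study has to have 55 participants with two end point". For a simple correlation, two-sided 5% and 80% power, the smallest detectable r is tanh((1.960 + 0.842)/sqrt(n - 3)). The shares past T2 are assumptions:

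| Share past T2 | n with change | Smallest detectable r |
|---|---|---|
| 0% | 55 | tanh(2.802/sqrt(52)) = 0.37 |
| 25% | 55 × 0.75 ≈ 41 | tanh(2.802/sqrt(38)) = 0.43 |
| 50% | 55 × 0.50 ≈ 28 | tanh(2.802/sqrt(25)) = 0.51 |

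**The case against.** The best counter-argument is that the table may simply be incomplete. It lists the step-test, waist circumference and the eating-behaviour form at BL only, while sections 3.1 and 3.4 between them place the physical test, waist and overeating behaviour at T1 and T2 as well. The RTWSE-19 row could be the same kind of slip, and work motivation at T1 and T2 might be meant to cover it. This is possible, but nothing in the protocol says so, and work motivation is not defined as self-efficacy. If the table is wrong, it still has to be corrected, because staff who follow it will not give the form again.

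Second, the word changes in aim 2 could attach only to the lifestyle items, with self-efficacy as a level. Sections 2, 3.6 and 3.9 would then agree. That is the less natural reading: aims 1 and 3 are built the same way, and there the word covers the whole list.

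Third, the level-or-change choice for x3 could be left to a statistical analysis plan, which is not at hand. That is true of the definition, but no analysis plan can supply a measurement that was never scheduled.

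Fourth, the figures rest on assumed inputs. The detectable correlations are bivariate, whereas section 3.9 plans three predictors, and the 55 was derived for change in 15D. They only indicate what late correction would cost. Likewise, the negative correlation between baseline and change does not fix the sign of the x3 coefficient; it shows only that the sign for baseline cannot be read as the sign for change. Section 3.14 also marks questionnaire collection in 2018 and 2019, so much follow-up probably lay ahead at the version date.

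What stands is that the issue is confined to one of three predictors in one secondary aim.

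**Conclusion.** The concern holds and should be fixed. As scheduled in section 3.6, the self-efficacy part of aim 2 cannot be answered, because RTWSE-19 yields no change score for any participant. This depends only on the table governing what is collected, not on any assumed number. Using the baseline score instead changes the question; over the assumed rho range, with equal SDs, at least 75% of the variance in change is left unexplained. How many participants can no longer supply a change is unknown and needs a count. The rest of aim 2, the primary question, aims 1 and 3 and the three sample-size calculations do not use RTWSE-19.

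**What to change.** Change the RTWSE-19 row in section 3.6 to BL, T1 and T2, using the form-filling already planned at 28 and 52 weeks. In section 3.9, define x3 once for everyone as the BL-to-T2 change in RTWSE-19. Participants past T1 but not T2 contribute this change. Those already past T2 are treated as missing it, and their number is reported. Baseline RTWSE-19 may be analysed too, but separately and labelled as such.

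If T2 collection is not possible, restate aim 2 and x3 for all participants as baseline self-efficacy. Choose between the two before analysis, from a count of participants not yet past T2, and do not mix levels and changes within one predictor.

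As a separate and smaller correction, reconcile the step-test, waist and eating-behaviour rows of section 3.6 with sections 3.1 and 3.4. These are not variables in aims 1 to 3 or in the section 3.9 models.

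The cost is one more 19-item form at two existing visits and a protocol amendment, with participants already past T2 lost from the x3 change analysis. The fallback costs only rewording, but gives up the question about change in self-efficacy.

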3.7 Register data

NAV and NUDB have reliable information about work participation and education data. The data will contain information about social benefits as sick leave, work assessment allowance, if the participant is registered as a job seeker, changing in work employment, income, about the work place and expected work time pr. Week, occupation code and about education. Collecting data at the end of the study and correlating with data from the foams, journal and qualitative interview.

3.8 Qualitative interview

Participants who complete 12 months of treatment on Muritunet will receive an invitation to participate in a focus group interview. The interview is carried in the T3 phase one to four years after finishing the stay at Muritunet. The interview will focus on health, life style changes, life quality and work participation. Each interview will last about one and a half to two hours. The group interview will consist of 6 to 8 people. The primary purpose is to get a complete picture of the complexity of returning to work, and how life style changes influence the process. The data collection has a

particular focus on the participants experience on what promotes and inhibits the process returning to work in due to their health, physical activity, life quality, workplace, diets and other factors that can contribute.

3.9 Analyse

The goal of this study is to explore the correlation between life style changing and work participation. Four secondary issues will result in using different ways of analyzing the data material. In this way, each issue can be investigated on their own, but also analyzed with each other.

The primary analyzing approach for this study is multivariate logistics regression analysis with a focus on the correlation between several independent variables (X) and dependent variables (Y). In the main issue Y= work, and X= physical activity (x1), diets (x2) and life quality (x3). Work divides into three categories; a) full time working, b) part time working, c) not working. In the secondary issue, is Y= life quality and X= physical activity (x1), diets (x2), and the belief in managing (x3).

In the quality research, thematic methods will be used to analyze the interviews. This method can catch the significant complexity in the text and is the most usual way to analyze a text in qualitative research. This way of analyzing consist of six steps. 1. Transcribing data, 2. Reading and re-reading the data, 3. Coding, 4. Search after subjects, 5. Define and give a name to the subjects, and 6. Choose to illustrate examples of different issues.

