2. T1, six months after the first stay at Muritunet. Data gathered from the journal, from self-reported forms, and from a physical test. The particular data package is; in and out date for the stay, diagnosis, health problems, work status, social benefits, changing in work status, work place, expected work time pr. Week and occupation code, work motivation, income, diet, physical capacity and activity, life quality and overeating behaviour.
3. T2, 12 months after the first stay at Muritunet. Data gathered from the journal, from self-reported forms, and from a physical test. The particular data package is; in and out date for the stay, diagnosis, health problems, work status, social benefits, changing in work status, work place, expected work time pr. Week and occupation code, work motivation, income, diet, physical capacity and activity, life quality and overeating behaviour.
4. T3, Focus group interview, one to four years after the participants finishing their stay at Muritunet.

5. T4, Data collecting from Norwegian patient register (NPR) and National Education database (NUDB). Will be collected once. Data collected are social benefits as sick leave, work assessment allowance, disability benefits, unemployment benefits, diagnosis for sick leave, changing in work employment, work place and expected work time pr. A week and occupation code.

Some participants will return to their work, but some will not. It will lead to variation for my chose of how to design methods and analyze the data material. Different ways will complete each other, and today it is common to use several methods and models in the same study.

Data analysis is chosen on the background of design and approaches. BL, T1, and T2 is a typical quantitative approach and will be analyzed both on its own, but also compared with data collected in T3 and T4. The qualitative interview will have open-ended questions, and the participants will get the opportunity to reflect on themes defined from the data collection earlier in the study.

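### Section 3.9 lists life quality under logistic regression, the only quantitative model it names, although the 15D is a numeric score; linear regression should be named for it

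*Protocol*

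**What the plan says.** Protocol section 3.9 sets the method: "The primary analyzing approach for this study is multivariate logistics regression analysis with a focus on the correlation between several independent variables (X". The sentence then refers to dependent variables in the plural, and two outcome lines follow in the same paragraph.

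- Work is the outcome of the main issue. It is divided into full-time, part-time and no work.
- Life quality is the outcome of the next one: "In the secondary issue, is Y= life quality and X= physical activity (x1), diets (x2), and the belief in managing (x3". No categories, cut-point or other model are given.

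The only other method in section 3.9 is thematic analysis of the interviews. The section does say, just before, "Four secondary issues will result in using different ways of analyzing the data material", and section 3.1 remarks that "today it is common to use several methods and models in the same study". Neither sentence names a model. Section 3.9 is not a complete list either: it has no outcome line for weight, which is the outcome of aim 3.

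Life quality is measured by "Quality of life (15D) [33" at BL, T1 and T2 (section 3.6). Physical activity and food behaviour are on the same schedule. "Return to work self- efficacy (RTWSE 19) [31" is scheduled at BL only. Section 3.10 plans the 15D on "a clinical and a statistically significant change on 0,02 this study has to have 55 participants with two end point" and puts the smallest relevant change at 0.015. Aim 2 in section 2 asks: "Will changes in physical activity, diets, and return to work self-efficacy correlate with life quality".

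**The concern.** On the natural reading, the life-quality line belongs to the model named two sentences before it. That model suits work, which has categories, but not a numeric score. A statistician who applied the usual binary or multinomial form would first have to group the 15D. Because no cut-points are fixed, they could be chosen after the data are seen. The answer to aim 2 would then depend partly on that choice, and information within each group would be discarded. The protocol defined categories for its other outcome and did not do so here.

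**Working it through.** **Step 1: the scale of the 15D.** Section 3.10 gives 55 participants, a change of 0.02, power of 80.7% and a 95% interval of 0.025 to 0.045. Treated as a mean change:

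- half-width = (0.045 − 0.025)/2 = 0.010
- SE = 0.010/1.96 = 0.0051
- SD = 0.0051 × √55 = 0.038
- power = Φ(change/SE − 1.96)
- at 0.02: Φ(3.92 − 1.96) = 97.5% (97% with the t distribution)
- at 0.015: Φ(2.94 − 1.96) = 84% (82% with the t distribution)

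The stated 80.7% is thus not reproduced at 0.02, and 0.02 lies outside the stated interval. That is a separate matter in section 3.10. What counts here is that these inputs make sense only for a mean change in a numeric score.

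**Step 2: which logistic models accept such a score.** Binary and multinomial logistic regression need a limited set of categories, so the 15D would have to be grouped. Ordinal logistic regression can use grouped values, but it can also treat each distinct score as its own ordered level, which needs no cut-points. Section 3.9 does not say which form is meant.

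**Step 3: what grouping would cost.** This is an illustration. From the protocol it takes only n = 55, which was planned there for a mean change and not for a regression. The assumptions, none of them in the protocol, are three independent normal predictors, one of them with partial correlation r to the outcome, equal-sized groups and a two-sided 5% test. With change as outcome, y = r·x₁ + √(1 − r²)·e. There were 2000 runs per row (Monte Carlo SE at most √(0.25/2000) = 1.1 points). Logistic models used the likelihood-ratio test and linear regression the t-test.

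| Outcome and assumption | Median split | Ordinal, thirds | Ordinal, fifths | Linear |
|---|---|---|---|---|
| Change, r = 0 (type I error) | 5.8% | 5.6% | 6.1% | 4.5% |
| Change, r = 0.30 | 42.6% | 52.5% | 56.6% | 58.9% |
| Change, r = 0.40 | 68.5% | 78.3% | 83.0% | 85.4% |
| Change, r = 0.50 | 88.9% | 94.4% | 96.8% | 97.4% |
| T2 score, r = 0.40, baseline correlation 0.5 | 62.8% | 75.5% | 81.3% | 84.8% |
| T2 score, r = 0.40, baseline correlation 0.7 | 55.6% | 72.1% | 79.8% | 85.6% |
| T2 score, r = 0.40, baseline correlation 0.85 | 47.5% | 64.3% | 76.8% | 85.7% |

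The T2 rows have baseline 15D as a covariate in every model. At r = 0.40 the loss against linear regression is:

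- fifths: from 85.4 − 83.0 = 2.4 to 85.7 − 76.8 = 8.9 points
- thirds: from 85.4 − 78.3 = 7.1 to 85.7 − 64.3 = 21.4 points
- median split: from 85.4 − 68.5 = 16.9 to 85.7 − 47.5 = 38.2 points

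**Step 4: ordinal logistic regression on ungrouped scores.** Under the same assumptions (600 runs, Monte Carlo SE at most 2 points), power for linear against ordinal was 58% and 59% at r = 0.30, 88% and 88% at 0.40, and 98% and 98% at 0.50, with change as outcome. With the T2 score at r = 0.40 it was 84% and 86% for a baseline correlation of 0.7, and 84% and 83% for 0.85. Without grouping there is no visible loss.

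**The case against.** The strongest reply is that section 3.9 does not tie life quality to logistic regression. It calls that model primary, announces different methods for the secondary issues, and introduces life quality as secondary. What is left would be an unnamed model for a secondary question, and a protocol may leave that to the SAP, which is not at hand. This stands in part: the wording permits another model. It names none, however, and it puts the life-quality line under a model that does not suit a numeric score. That is a poor fit in what the protocol states, not merely missing detail.

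Three stronger readings are tempting, and the documents do not support them.

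- A reader might infer that section 3.9 forces the 15D into categories. It does not: ordinal logistic regression on the ungrouped scores needs no cut-points and performs about as well as linear regression (step 4).
- A reader might infer that the study stands to lose up to 38 points of power. That figure belongs to a median split with an assumed baseline correlation of 0.85, and the protocol proposes no median split, thirds or fifths.
- A reader might infer that linear regression would make results directly comparable with the 0.02 and 0.015 of section 3.10. Those are changes over time, whereas a slope is in 15D units per unit of a predictor. The gain is only that the result is on the 15D scale.

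**Conclusion.** The point holds in a limited form. Section 3.9 lists a numeric score under the only quantitative model it names, and the common forms of that model would need cut-points that the protocol does not fix. This mismatch rests on the text alone.

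The size of the harm depends on how the analyst would proceed: none to speak of with an ordinal model on ungrouped scores, small with five groups, large with a median split. All power figures rest on assumed correlations and on independent normal predictors. The weight is minor to moderate, because aim 2 is a secondary question in an exploratory study and a short change of wording settles it.

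**What to change.** In section 3.9, limit ordinal or multinomial logistic regression to three-category work, and add: *15D at T2 will be analysed as a continuous score by linear regression on baseline 15D, change from BL to T2 in physical activity, change from BL to T2 in diet, and baseline RTWSE-19; coefficients will be given with 95% confidence intervals in 15D units.* Using the changes in physical activity and diet follows the wording of aim 2. If the sponsor prefers a logistic model, its form and any cut-points should be fixed and justified before the data are seen.

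The cost is one sentence and the usual check of residuals, because the 15D is a bounded score. All the measurements are already scheduled in section 3.6, so no new data are needed.

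One matter stays open. RTWSE-19 is scheduled at BL only and can enter only as its baseline value, while aim 2 asks about change in self-efficacy. Aim 2 and section 3.6 must be reconciled separately; this sentence does not do it.
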